*****Perform CMH test*****  
*****/
```

*** Step I: Obtain Mantel-Haenszel estimate of the common odds ratio adjusted for &Strata ***.

```
PROC SORT DATA=&datain;  
by &Visit &Imput;  
RUN;
```

```
PROC FREQ DATA=&datain;  
TABLES &Strata*&Trt*&Resp / CMH;  
ODS OUTPUT COMMONRELRISKS=comrrout;  
BY &Visit &Imput;  
RUN;
```

```
*** Log-transform odds ratio estimates  
and obtain standard error from confidence intervals ***;  
DATA ormh_t; SET comrrout(WHERE=(StudyType="Case-Control"));  
log_or_mh_value=log(VALUE);  
log_or_mh_se=(log(UPPERCL)-log(LOWERCL))/(2*quantile('Normal',.975));  
RUN;
```

```
*** Combine proportion estimates;  
PROC SORT DATA=ormh_t; BY &Visit &Imput; RUN;
```

```
PROC MIANALYZE DATA=ormh_t alpha=0.1;
MODELEFFECTS log_or_mh_value;
STDERR log_or_mh_se;
BY &Visit;
ODS OUTPUT PARAMETERESTIMATES=log_cmh;
RUN;
```

```
data &dataout_cmh ;
set log_cmh ;
Common_or = exp(Estimate);
*Or_upper = exp(Estimate+quantile('Normal',.95)*StdErr);
*Or_lower = exp(Estimate-quantile('Normal',.95)*StdErr);
e_lcl = exp(LCLMean);
e_ucl = exp(UCLmean);
Keep &Visit Common_or e_lcl e_ucl;
run;
```

```
PROC FREQ DATA=&datain;
TABLES &Strata*&Trt*&Resp / CMH;
ODS OUTPUT CMH=cmh;
BY &Visit &Imput;
RUN;
```

```
%if &method=1 %then %do;
/*****Step II/Option 1: To obtain p-values, perform CMH test
by applying Wilson-Hilferty transformation to the CMH statistic*****/
*** Apply Wilson-Hilferty transformation to the CMH statistic and
standardize the resulting normal variable;
DATA cmh_wh; SET cmh(WHERE=(AltHypothesis="General Association"));
cmh_value_wh=((VALUE/DF)**(1/3) - (1-2/(9*DF)))/SQRT(2/(9*DF));
cmh_sterr_wh = 1.0;
RUN;
*** Combine results;
PROC MIANALYZE DATA=cmh_wh;
by &Visit;
ODS OUTPUT PARAMETERESTIMATES=mian_cmh_wh;
MODELEFFECTS cmh_value_wh;
STDERR cmh_sterr_wh;
RUN;
*** Compute one-sided p-value;
DATA &dataout_p; SET mian_cmh_wh;
IF tValue > 0 THEN Probt_WH = Probt/2;
ELSE Probt_WH = 1-Probt/2;
KEEP &Visit Probt_WH;
RUN;
%end;
```

```
%if &method=2 %then %do;
/*****Step II/Option 2: To obtain p-values, perform CMH test
by applying Rubin & Li et al's transformation to the CMH statistic*****/
DATA cmh_rub; SET cmh(WHERE=(AltHypothesis="General Association"));
KEEP &Visit &Imput DF Value;
RUN;
```

```
PROC SORT DATA=cmh_rub ;
```

```
BY &Visit &Imput;
RUN;
```

[figure not shown]
```
*** Implement pooling procedure described in equations (3) and (4);
```

[figure not shown]
```
PROC IML;
USE cmh_rub ;
READ ALL VAR {Value} INTO chval;
READ ALL VAR {&Visit} INTO vis;
Read ALL VAR "DF";
close;
uvis=unique(vis);
n_vis=ncol(uvis);
df=unique(df);
n=nrow(chval);
m=n/n_vis;
Prob_Rub={};
VisitN={};
do i=1 to n_vis;
VisitN=VisitN//uvis[1,i];
st=(i-1)*m+1;
en=i*m;
cvalroot_m = sum(chval[st:en]##0.5)/m;
cval_m = sum(chval[st:en])/m;
a=(chval[st:en]##0.5-j(m,1,1)*cvalroot_m)##2;
rx = sum(a)*(1+1/m)/(m-1);
Dx=(cval_m/df - (m+1)/(m-1)*rx)/(1+rx);
df_den=(df**(-3/m))*(m-1)*(1+1/rx)**2;
Pval1=1-CDF("F",Dx,df,df_den);
Prob_Rub=Prob_Rub//Pval1;
end; *endc;
create &dataout_p var {Prob_rub VisitN} ;
APPEND;
close &dataout_p;
RUN; QUIT;

%end;
%mend ;
```

Before calling the above macro, first create a ‘Strata’ variable for the interaction term of stratified baseline binocular DCNVA and age group <Stratified baseline binocular DCNVA by age group interaction>, which will result in four strata/levels. The response variable should be dichotomized based on the multiply imputed data set created by the Five Macros &jobname._datafinal. Set ‘method=2’ as Rubin and Li et al.’s approach will be used. The macro contains three output data sets: &dataout_sum contains summary statistics of the binary variable; &dataout_cmh contains point estimate(s) and standard error(s) of the combined CMH test; &dataout_p includes the corrected p-value(s) after combining CMH statistics from the multiply imputed data sets.

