##### **12.5.1 Efficacy endpoint**

The secondary efficacy endpoint, the proportion of subjects aged 45 to 55 years achieving 75 or more ETDRS letters in binocular DCNVA at Month 3, is based on the data observed in the FAS population, according to the treatment group patients was randomized and the DCNVA stratum that was assigned at randomization. The comparison between the two treatment groups will be performed using stratified Cochran-Mantel-Haenszel test at one-sided 5% level of significance.

Assuming the following hypotheses will be tested:

$$H_0: \delta_2 = 0 \text{ vs. } H_a: \delta_2 > 0$$

where  $\delta_2$  is the difference of proportion of subjects achieving 75 or more ETDRS letters in binocular DCNVA between the UNR844-C1 and placebo at Month 3.

The estimand for the secondary efficacy endpoint is closely related to the estimand for the primary efficacy endpoint. For subjects who has a DCNVA assessment at Month 3, the observed letter score will be used to derive the endpoint of achieving 75 or more ETDRS letters or not. For subjects who has no DCNVA assessment at Month 3, the predicted value of the estimand

for the primary efficacy endpoint will be used to derive the endpoint of achieving 75 or more ETDRS letters or not.

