2.5.2 Statistical hypothesis, model, and method of analysis

The primary efficacy endpoint, change from baseline in binocular DCNVA, will be analyzed at Month 3 based on the data observed in the FAS population, according to the treatment group subjects were randomized to and the strata that were assigned at randomization. The strata information will be based on the data obtained from Interactive Response Technology (IRT) that was utilized for randomization. The comparison between the two treatment groups will be performed using a two group t-test at one-sided 5% level of significance.

Assuming general linear model for change from baseline in binocular DCNVA, the following hypotheses will be tested:

$$H_0: \delta_1 = 0 \text{ vs. } H_a: \delta_1 > 0$$

where δ_1 is the difference of change from baseline in numbers of letters read correctly between the UNR844-Cl and placebo at Month 3.

A mixed effect model repeat measurement (MMRM) model with the change from baseline in binocular DCNVA will be fitted. The model will include the change from baseline in binocular DCNVA as the dependent variable, binocular DCNVA at baseline (on its original continuous scale) as the covariate, treatment group and age group stratum at randomization, assessment visit, interaction of treatment group and assessment visit as the fixed effects and subject as a random effect. For subjects who do not have a binocular DCNVA assessment at Month 3, the predicted values of the individual subject based on the multiple imputation will be used as

dependent variable for the primary endpoint analysis and one of the supportive analysis ([Section 2.5.3](#)).

The p-value will be adjusted to one-sided, and is calculated as follows:

- $0.5 \times (\text{original two-sided p-value})$ if the least squares mean difference of UNR844 versus placebo is greater than 0
- $1 - 0.5 \times (\text{original two-sided p-value})$ if the least squares mean difference of UNR844 versus placebo is smaller than or equal to 0.

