2.7.2 Statistical hypothesis, model, and method of analysis

The analysis of the secondary efficacy endpoint is based on the data observed in the FAS population, according to the treatment group subjects was randomized and the DCNVA stratum that was assigned at randomization. The comparison between the two treatment groups will be performed using stratified Cochran-Mantel-Haenszel (CMH) test at one-sided 5% level of significance, with stratified baseline DCNVA and age group as the stratification factors. Alternatively, if the cell count for any of the strata is too small (e.g., <5), the analysis will be done separately for each of the two stratification factors.

Assuming the following hypotheses will be tested:

$$H_0: \delta_2 = 0 \text{ vs. } H_a: \delta_2 > 0$$

where δ_2 is the difference of proportion of subjects achieving 75 or more ETDRS letters in binocular DCNVA between the UNR844-CI and placebo at Month 3.

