3.1.2 Secondary endpoints

Assuming the proportion of subjects achieving 75 or more ETDRS letters in binocular DCNVA at Month 3 are 40.5% and 10.5% for UNR844-CI and placebo, respectively, based on the results of the prior study in presbyopic subjects, 66 subjects (33 in each arm) aged 45 to 55 years are required to be completed to achieve an approximate power of 82% at 5% (one-sided) significance level.

4 Change to protocol specified analyses

Not applicable.

5 Appendix

Statistical methods are described in the main part of the clinical study report. This appendix provides further details on the statistical derivation and practical implementation.

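### The code selected for the secondary responder endpoint prints a two-sided, direction-blind p-value, although the plan specifies a one-sided 5% CMH test

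*SAP*

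**What the plan says.** Protocol 12.5.1 tests δ2 = 0 against δ2 > 0 with a "stratified Cochran-Mantel-Haenszel test at one-sided 5% level of significance". SAP 2.7.2 repeats this: "stratified Cochran-Mantel-Haenszel (CMH) test at one-sided 5% level of significance". The data-analysis part of the protocol summary gives the direction, a higher responder proportion on UNR844-CI. The sample-size text is one-sided too; 33 completers per arm are said "to achieve an approximate power of 82% at 5% (one-sided) significance level".

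SAP 5.2.2 supplies a macro with two ways of pooling the CMH result over imputed data sets, and selects method=2. Its input is the general-association statistic ("DATA cmh_rub; SET cmh(WHERE=(AltHypothesis='General Association") and its p-value line is "Pval1=1-CDF('F',Dx,df,df_den". The value is stored unchanged as `Prob_Rub`. The text says the output data set "includes the corrected p-value(s) after combining CMH statistics from the multiply imputed data sets" and adds nothing on sidedness.

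The primary analysis is handled differently. SAP 2.5.2 says "The p-value will be adjusted to one-sided, and is calculated as follows" and gives a rule based on the sign of the mean difference; SAP 5.2.1 repeats such a rule. SAP section 4 declares no change from the protocol's analyses.

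**The concern.** With two arms and a binary response, the general-association CMH statistic is a 1-df chi-square with no sign. Method=2 averages the statistics and their non-negative square roots and takes an upper F tail. No line of that branch reads which arm has more responders, so the result is a two-sided p-value.

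Method=1, which is not selected, does not repair this. Its step labelled one-sided ("IF tValue > 0 THEN Probt_WH = Probt/2") uses the sign of the Wilson-Hilferty transform of the same unsigned chi-square. That sign reflects how large the statistic is, not which arm is better.

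Two things are at stake if `Prob_Rub` is read against 0.05. A result that meets the specified one-sided test is missed whenever `Prob_Rub` lies between 0.05 and 0.10 in favour of UNR844-CI; the macro's own 90% odds-ratio interval would then usually exclude 1, so one endpoint would carry two conflicting results. And a placebo advantage can print p < 0.05, with its direction visible only in the separately reported proportions and odds ratio.

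**Working it through.** **Inputs.** Responder rates 40.5% and 10.5%, 33 completers per arm, stated power 82% at one-sided 5% (Protocol 12.8.2, SAP 3.1.2). Test formulas are from the SAP 5.2.2 macro.

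**1. The plan's own figure.** Difference 0.300; mean rate 0.255.
- Null SE = √(0.255 × 0.745 × 2/33) = 0.1073.
- Alternative SE = √[(0.405 × 0.595 + 0.105 × 0.895)/33] = 0.1007.
- Power = Φ[(0.300 − c − z × 0.1073)/0.1007], with c = 0, or c = 1/33 with continuity correction.

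| | One-sided 5% (z = 1.645) | Two-sided 5% (z = 1.960) |
|---|---|---|
| No correction | 89.0% | 81.3% |
| Continuity-corrected | 82.3% | 72.2% |

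The stated 82% reproduces as the corrected one-sided figure, which fits its one-sided label. The uncorrected two-sided figure is also close, so the number alone does not settle the sidedness.

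**2. What method=2 computes.** For m imputed chi-squares with df = 1:
- r = (1 + 1/m) × sample variance of the square roots
- D = [mean chi-square − r(m + 1)/(m − 1)]/(1 + r)
- v = (m − 1)(1 + 1/r)²
- p = P(F(1, v) > D)

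With negligible between-imputation variance, z = 1.645 gives p = 0.100 and z = 1.960 gives p = 0.050, the two-sided values. One hundred values of z centred at +1.7 give 0.090 (one-sided 0.045). Values centred at −2.5, placebo better, give 0.012 (one-sided 0.994). Reversing every sign leaves p unchanged.

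**3. Exact enumeration.** 33 per arm, unstratified, complete data, CMH statistic with the N − 1 variance:

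| | One-sided 5% test | `Prob_Rub` read against 0.05 |
|---|---|---|
| Power, 40.5% vs 10.5% | 90.3% | 81.9% |
| Null at 25.5%, rejection towards UNR844-CI | 5.2% | 2.3% |
| Null at 25.5%, any rejection | 5.2% | 4.6% |
| Rates reversed, any rejection | about 0% | 81.9% |

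The coded p lies between 0.05 and 0.10 in favour of UNR844-CI in 8.4% of trials at the planned rates. With the rates reversed, all but a negligible share of the rejections favour placebo.

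**4. Simulations at the planned rates.**
- Four equal strata (assumed), 40,000 trials: 88.8% one-sided, 81.1% as coded, conclusion changed in 7.7%.
- Method=2 pooling, 36 per arm, 3 per arm imputed under MAR, 20 imputations (all assumed), 8,000 trials: 89.4%, 81.9% and 7.5%.

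**5. One worked result: 10/33 on UNR844-CI, 4/33 on placebo.**
- Expected UNR844-CI responders 7; variance = 33 × 33 × 14 × 52/(66² × 65) = 2.80.
- z = 3/√2.80 = 1.793; chi-square 3.214.
- One-sided p = 0.036; coded p = 0.073.
- Odds ratio = (10 × 29)/(23 × 4) = 3.15, 90% CI 1.07 to 9.25, which excludes 1.
- Method=1: (3.214^(1/3) − 7/9)/√(2/9) = 1.48, upper tail 0.069. The result 4/33 vs 10/33 gives the same 0.069.

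**The case against.** The strongest reply is that this is an unwritten step and not a wrong test. The governing rule stands in the main text, the code is an implementation appendix, and nothing says `Prob_Rub` is compared with 0.05. The macro's intervals are at 90%, the two-sided counterpart of one-sided 5%. Read at 0.10, with direction taken from the odds ratio, `Prob_Rub` gives the specified decision. The proportions and odds ratio are printed, so a placebo advantage would be seen. The coded test still has 81–82% power, close to the stated figure. SAP 2.6 names no key secondary objective, and the error is conservative.

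Much of this is true and limits the harm. The harm does depend on the direct reading. The continuity-corrected pair explains the 82% but is not the power of the coded test, because the macro requests no correction. The four-stratum simulation ignores the SAP 2.7.2 fallback for small cell counts: 33/4 × 0.105 is about 0.9 expected placebo responders per stratum, so if the fallback refers to 2×2 cells it would almost certainly apply. The sidedness problem is the same under the fallback.

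The reply does not remove the defect. The SAP presents the method=2 output as the finished p-value, while the primary analysis has its conversion written out twice. A choice between p and p/2 left until after unmasking could decide the result.

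**Conclusion.** The concern holds. Followed as written, SAP 5.2.2 delivers a two-sided p-value that ignores direction for a test that both documents define as one-sided at 5%.

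Read against 0.05, this roughly halves the error rate towards UNR844-CI, costs about 8 percentage points of power at the planned rates, and changes the conclusion in 7.5% to 8.4% of trials. These figures assume that direct reading and the planned rates. The exact ones also assume complete, unstratified data; the simulations rest on the stratum sizes and missingness stated with them. The mismatch itself is visible in the code and needs none of these assumptions.

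It should be fixed, but its reach is limited: one secondary endpoint, conservative for a claim of benefit, recoverable from the printed output, with no effect on the primary test.

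**What to change.** Before unmasking, add to SAP 2.7.2 and to the method=2 branch: one-sided p = `Pval1`/2 if the pooled treatment effect favours UNR844-CI, otherwise 1 − `Pval1`/2.

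Take the direction from the pooled Mantel-Haenszel odds ratio that the macro already produces. State the coding of `&Trt` and `&Resp` so that a value above 1 means more UNR844-CI responders. The macro does not fix this order now, and the opposite order would invert the p-value.

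Two alternatives are less suitable. Method=1 is also blind to treatment direction. A one-sided Wald test of the pooled log odds ratio has a direction but is not the CMH test the plan names; it gives 0.040 instead of 0.036 in the worked result.

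The cost is one sentence of SAP text, a stated coding and a few lines of code, with no effect on patients, data or timeline.

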5.3 Rule of exclusion criteria of analysis sets

The following table provides the definitions of the protocol deviations of the study, together with the exclusion rules.

Table 1 Protocol Deviations

PD ID	Deviation Text	Data exclusion
INCL01	Informed consent not obtained	Exclude from all analysis sets

PD ID	Deviation Text	Data exclusion
INCL02	Phakic presbyopic male or female subjects aged 45 to 65 years at baseline	Include in all analysis sets
INCL03	DCNVA at 40 cms less than 70 ETDRS letters	Include in all analysis sets
INCL04	Near add of +1.00D or greater	Include in all analysis sets
EXCL01	Distance visual acuity of less than 85 ETDRS letters at 4m	Include in all analysis sets
EXCL02	Distance refractive error spherical equivalent greater than +4.0D or less than -4.0D	Include in all analysis sets
EXCL03	Astigmatism of greater than 1.25D	Include in all analysis sets
EXCL04	Difference of greater than 0.50D between manifest and cycloplegic refraction spherical equivalent	Include in all analysis sets
EXCL05	Anisometropia of greater than 0.75D	Include in all analysis sets
EXCL06	Clinically significant congenital or acquired changes to the lens or iris in either eye or clinically significant phacodonesis.	Include in all analysis sets
EXCL07	Undilated pupillary diameter of less than 2.5 mm in either eye	Include in all analysis sets
EXCL08	Unequal pupil diameters with a difference of greater than 1 mm between eyes	Include in all analysis sets
EXCL09	Non-circular pupil assessed related to a pathological cause	Include in all analysis sets
EXCL10	Contraindication to pupil dilation	Include in all analysis sets
EXCL11	Prior history or current diagnosis of any accommodative issues	Include in all analysis sets
EXCL12	Secondary cause of presbyopia in either eye	Include in all analysis sets
EXCL13	Any active ocular infection in either eye at screening or baseline.	Include in all analysis sets
EXCL14	History of idiopathic or autoimmune uveitis in either eye.	Include in all analysis sets
EXCL15	Ocular surface disease from any cause that is greater than mild in severity and is not controlled by OTC artificial tears	Include in all analysis sets

PD ID	Deviation Text	Data exclusion
EXCL16	History or current diagnosis of treated or untreated glaucoma of any type.	Include in all analysis sets
EXCL17	History of ocular trauma in either eye.	Include in all analysis sets
EXCL18	Prior intraocular surgery or laser surgery including prior cataract extraction.	Include in all analysis sets
EXCL19	Planned intraocular or extra-ocular surgery (e.g., cataract extraction or refractive surgery) in either eye during the study period.	Include in all analysis sets
EXCL20	History of or current use of [REDACTED]	Include in all analysis sets
EXCL21	Prior participation in the EV-C-002 study or prior use of UNR844-C1.	Include in all analysis sets
EXCL22	Hypersensitivity to any of the study drugs or its inactive ingredients	Include in all analysis sets
EXCL23	Use of any medication known to affect accommodation, pupils or intraocular pressure	Include in all analysis sets
EXCL24	Use of other investigational drugs within five half-lives or within 30 days of the screening visit	Include in all analysis sets
EXCL25	Prior therapy for presbyopia other than optical correction	Include in all analysis sets
EXCL26	History of clinically significant cardiac abnormality	Include in all analysis sets
EXCL27	History of diabetes mellitus	Include in all analysis sets
EXCL28	History of malignancy of any organ system within 6 months of screening	Include in all analysis sets
EXCL29	Any ocular or systemic condition that, in the opinion of the investigator, would jeopardize subject safety	Include in all analysis sets
EXCL30	Pregnant or nursing (lactating) women at screening	Include in all analysis sets
EXCL31	Women of child-bearing potential, unless they are using basic methods of contraception during the course of the study	Include in all analysis sets
EXCL32	Subjects in a dependent or unequal relationship with the Sponsor or study site staff	Include in all analysis sets

PD ID	Deviation Text	Data exclusion
TRT01	Randomized but wrong IP administered during the study	Include in all analysis sets
TRT02	Investigational or other study treatment dose adjustments and/or interruptions made	Include in all analysis sets
TRT03	Subject missed a visit not allowed in the study	Include in all analysis sets
OTH01	Any other protocol deviation without impact on the safety of the patient	Include in all analysis sets
COMD01	Prohibited medication and/or procedure as per protocol	Include in all analysis sets
COMD02	Prohibited medication change as per protocol	Include in all analysis sets
WITH01	Subject withdrew consent but continue to receive study medication.	Include in all analysis sets
